M	
Statistical & Analytical Plan and Methodology
 
The primary objective of this descriptive study is to determine if there are statistically significant differences in PFS to first line systemic therapy between subjects with recurrent/metastatic disease and NTRK fusion versus those without a known NTRK fusion.
 
The two groups will be matched with respect to histological subtype, sex, age (+/-5 years), and pathological tumor-node-metastasis (TNM) stage.
 
The Kaplan-Meier method will be employed for the analysis of PFS. A nonparametric test, such as the log-rank test, based on the Kaplan-Meier estimator for survival curves, will be employed to assess the association between PFS and the presence of NTRK fusion. In addition, predictive modeling, including Cox proportional hazards models with NTRK fusion as a predictor may also be used to estimate the relative risk of the exit-event of subjects with tumors with NTRK fusion versus subjects with tumors without known NTRK fusion. If the data allow it, other types of predictive modeling may also be explored. If the proportionality of hazard assumption fails, then parametric approaches will be used.
		

	
Given the rarity of NTRK fusions among subjects with solid tumors, the sample size for this study will not be driven by powering the study. A post hoc power calculation will be provided. Clinically relevant changes will be defined as increases in median survival times that are greater than 30%, regardless of confidence interval width.
 
An assessment of the impact of certain covariates will be conducted by comparing their associated hazard ratios from the Cox proportional hazard (or parametric model) analysis.
 
Descriptive statistics will be employed to define demographic and treatment outcome, as well as overall frequency of NTRK fusions in the screened population. This will include exploration of potential effects on subject's treatment outcomes of different forms of NTRK fusions and of other genetic alterations.

--	--

Timelines	

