M	
Planned Study Timelines:
 
 
1. Enrolment rate (patients per month): 300 patients/months
 
2. Planned estimate of treatment duration: not applicable
 
3. Submission date to health authority/ethics: not applicable
 
4. Start of subject enrolment: December 2018
 
5. End of Subject enrolment: December 2019
 
6. All patients completed: December 2019
 
7. End of Study: March 2020
 
8. Report (as described in the contract): Report every 3 months
 
9. Planned publication/presentation: June 2020
 

Limitations	
O	
Criteria for selection of evaluable cases:
 
All patients:
 
who have received at least one systemic anti-cancer therapy for locally advanced/unresectable or metastatic disease for which there is available outcome information in terms of PFS,
 
who have tumor material tested by IHC for NTRK gene fusions,
 
will be included in the analysis.

M	Interim Analyses (if applicable)

	
Interim analyses will be the subject of periodic reports based upon collection of data on first 1,000, 2,000 patients and a final analysis will be conducted after completion of the whole data set analysis.
 
At each interim analyses, the proportion of NTRK-rearranged cases will be estimated in order to assess the feasibility of a comparative analysis with matched controls.

M	
Number of Evaluable Patients (estimate): it is anticipated to collect data on 3,700 patients

M	
Sample Size Assumptions/Target Number of Valid Cases (incl. Power and Confidence)
 
No sample size estimate has been calculated. It is assumed that a sample size of 3,700 patients should be sufficient to address the primary objective of this study.

0	
Statistical analyses
 
 
Quantitative variables will be described using mean and standard deviations if the normality assumption is satisfied, else other descriptive statistics (median, range, quartiles) will be reported.
 
Qualitative variables will be described using frequency, percentage and 95% confidence interval (binomial law).
 
Survival endpoints will be analysed using the Kaplan-Meier method. The median survival rates will be reported with a 95% confidence interval. Median follow-up will be calculated using the reverse Kaplan-Meier method.
 

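### The post hoc power calculation has no named effect; if run at the observed effect, it would only restate the p-value

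*Combined protocol and SAP*

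**What the plan says.** All references are to the combined protocol and SAP.

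- **Statistical & Analytical Plan and Methodology.** The primary objective is worded as a significance test: "to determine if there are statistically significant differences in PFS to first line systemic therapy", fusion versus no known fusion. The method is "A nonparametric test, such as the log-rank test, based on the Kaplan-Meier estimator for survival curves". Cox models are optional.
- **Same section, on size.** Because fusions are rare, "the sample size for this study will not be driven by powering the study". The next sentence is "A post hoc power calculation will be provided". No effect, alpha, sidedness, event count or use for the result is attached to it.
- **Same section, directly after.** "Clinically relevant changes will be defined as increases in median survival times that are greater than 30%, regardless of confidence interval width". This is a rule for clinical relevance and is not linked to the power calculation.
- **Same section, on matching.** "The two groups will be matched with respect to histological subtype, sex, age (+/-5 years), and pathological tumor-node-metastasis (TNM) stage". The number of controls per case is not given.
- **Sample Size Assumptions.** "No sample size estimate has been calculated", followed by "It is assumed that a sample size of 3,700 patients should be sufficient to address the primary objective of this study".
- **Interim Analyses.** The reports at 1,000 and 2,000 patients estimate the proportion of fusion cases to judge whether a matched comparison is feasible. No minimum number of cases or events is set.

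**The concern.** Post hoc power is the only power statement planned for a significance-based objective. The term normally means power evaluated at the estimate the study has just produced. That version carries no information beyond the p-value: every non-significant result shows power below 50%, and every significant one shows at least 50%.

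This matters because a null result is a realistic outcome in a rare-fusion study. The reader will then need to know whether the data argue against a difference or whether there were too few fusion patients to tell. Observed-effect power looks like an answer and is not one. Since the effect is left open until results are known, the plan permits the uninformative version.

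**Working it through.** The plan states no power, event count or sample-size derivation, so there is no figure of its own to reproduce.

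**Inputs from the plan:** 3,700 patients; a median increase above 30%; reports at 1,000 and 2,000 patients and at the end; fusion incidence stated as unknown (Rationale).

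**Assumed here, because the plan is silent:** two-sided alpha 0.05; exponential PFS; the 30% rule applied to PFS; 1:1 or 1:4 matching; a PFS event in every fusion patient and control (best case); matching ignored in the variance; fusion frequency from 0.3% to 5%.

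**Step 1. Power at the observed effect.** With z_p the normal deviate for the two-sided p-value, power = Phi(z_p − 1.96) + Phi(−z_p − 1.96). Neither the event count nor the HR appears in it.

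| p | z_p | Power |
|---|---|---|
| 0.05 | 1.960 | 50% |
| 0.20 | 1.282 | 25% |
| 0.50 | 0.674 | 10% |

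**Step 2. The same p-value at very different study sizes.** Fix p = 0.30 with 1:1 groups. With 20 events in total this corresponds to an observed HR of 0.629; with 1,000 events, to 0.937. Observed-effect power is about 18% in both.

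Now hold the effect at HR 1/1.3 = 0.769 and use power = Phi(ln 1.3 × sqrt(D/4) − 1.96), with ln 1.3 = 0.2624 and D the total events:
- D = 20: Phi(0.587 − 1.96) = about 8%.
- D = 1,000: Phi(4.148 − 1.96) = about 99%.

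The fixed-effect figure separates the two studies and the observed-effect figure does not.

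**Step 3. Fixed-effect power over assumed fusion frequencies.** With d fusion events and k controls per case, SE = sqrt(1/d + 1/(k d)), and power = Phi(0.2624/SE − 1.96). At 1% and 1:4, d = 37, SE = sqrt(1.25/37) = 0.184, and Phi(1.427 − 1.96) = 30%. The smallest median ratio detectable with 80% power is exp(2.80 × SE), and the detectable HR is its reciprocal.

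| Frequency (assumed) | d = frequency × 3,700 | Power 1:1 | Power 1:4 | Detectable ratio 1:1 | Detectable ratio 1:4 (HR) |
|---|---|---|---|---|---|
| 0.3% | 11.1 | 9% | 12% | 3.28 | 2.56 (0.39) |
| 1% | 37 | 20% | 30% | 1.92 | 1.67 (0.60) |
| 2% | 74 | 36% | 52% | 1.58 | 1.44 (0.69) |
| 5% | 185 | 71% | 89% | 1.34 | 1.26 (0.79) |

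**Step 4. Events needed for 80% power at HR 0.769 (Schoenfeld).**
- 1:1: 457 events in total, about 229 in fusion patients; 229/3,700 = 6.2%.
- 1:4: 713 events in total, about 143 in fusion patients; 143/3,700 = 3.9%.

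**The case against.** The strongest reply is that the sentence does not say the observed effect will be used. The next sentence supplies a fixed reference, a median increase above 30%, and power at that effect with the achieved events would also be post hoc, would not be a function of p, and would describe what the study could detect. This stands. A reader might infer that the planned calculation necessarily restates the p-value, but the text supports this only conditionally. It does not remove the point, because nothing connects the 30% rule to the power calculation and the uninformative version remains open.

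Three other inferences also go further than the documents:
- **That post hoc power is offered to justify 3,700 patients.** It is not. Sufficiency is stated as a bare assumption in a different section, and the methods section disclaims sizing by power.
- **That the study is underpowered.** The fusion incidence is stated as unknown. Calling fusions rare points to the upper rows of the Step 3 table but sets no ceiling, and at 5% with 1:4 matching power would be 89%.
- **That event numbers will be withheld.** The plan reports fusion frequency and 95% CIs for medians. It simply does not plan a statement of what the comparison could detect.

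It is also fair to say that the study is called descriptive and that no decision or stopping rule hangs on this sentence. That limits the harm to misreading a supplementary number, although the objective is still framed as a test of significance.

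**Conclusion.** The point holds in conditional form. The effect for the post hoc power calculation is unspecified; on the usual meaning of the term, the result is a transformation of the p-value and cannot distinguish no difference from too few fusion cases. The mapping in Step 1 depends on the assumed two-sided alpha of 0.05; at any other alpha the numbers change but the one-to-one relation does not.

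The fixed-effect powers illustrate why the choice of effect matters and are not estimates of this study's power. They rest on the assumed frequencies, matching ratio and exponential PFS, and on every patient having an event; fewer events would lower them. This is a worthwhile, inexpensive improvement and does not invalidate the design. Rarity is a fair reason not to size the study by power, but not a reason to leave detectability unstated.

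**What to change.** Replace the post hoc power sentence with two commitments:

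1. The Cox HR for NTRK fusion with its 95% CI is always reported. At present Cox modelling is optional, and the confidence intervals promised for survival endpoints are for medians.
2. At the 1,000 and 2,000 patient reports and at the end, a short table gives the number of fusion cases and PFS events, the power at the plan's own 30% longer median (HR about 0.77 under exponential PFS), and the detectable HR. Power is never computed at the observed effect.

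Fix alpha, sidedness and the matching ratio in writing before the PFS comparison is run, and state that the 30% rule refers to PFS if that is what is meant.

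No extra patients or data are needed. The cost is one table and a few sentences, and the stated adequacy of the study may look less favourable.

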**Additional request details**

M	Primary Endpoint/ objective is safety	No
M	Study exploring new combinations, alternative dosing/dosing schedules or new formulations	No

M	Study with clinical pharmacology objectives, including biomarker, pharmacokinetic (PK) or pharmacodynamics (PD) evaluations	No
O	Author	[name], PhD Institut Bergonie Early Phase Trials and Sarcoma Units [name] Phone: [name] Fax: [name] E-mail: [contact]
O	Investigator Operations Manager email	[name], PhD  Head of Clinical Research Unit: [name] Institut Bergonié – Bordeaux Phone :[name] E-mail : [contact]
M	Study support	Financial
M	Study is financially supported by other organizations	No

Rationale and objectives	
O	Please explain why this study is non-blinded (if applicable): This is a retrospective study.
M	Study Type and Design  This multicenter, retrospective study has a primary objective to assess the impact of NTRK gene fusions on the PFS of first-line systemic therapy for the treatment of locally advanced/unresectable or metastatic solid tumors.  Control subjects will be matched based on the characteristics of the NTRK fusion study population to the greatest extent possible.
M	Rationale  The tropomyosin receptor kinase (Trk) receptor family comprises 3 transmembrane proteins referred to as Trk A, B and C (TrkA, TrkB and TrkC) receptors that are encoded by the NTRK1, NTRK2 and NTRK3 genes, respectively. These receptor tyrosine kinases are expressed in human neuronal tissue and play an essential role in the physiology of development and function of the nervous system through activation by neurotrophins. Gene fusions involving NTRK genes lead to transcription of chimeric Trk proteins with constitutively activated or overexpressed kinase function conferring oncogenic potential. These genetic abnormalities have recently emerged as targets for cancer therapy, because novel compounds have been developed that are selective inhibitors of the constitutively active rearranged proteins. Developments in this field are being aided by next generation sequencing methods as tools for unbiased gene fusions discovery. However, the incidence

	of NTRK aberrations in solid tumors is unknown as well as the natural history of NTRK-rearranged tumors.

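### The rule for calling a PFS difference clinically relevant uses the point estimate alone, so with few fusion cases chance will often earn the label

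*Combined protocol and SAP*

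**What the plan says.** All references are to the combined protocol and SAP.

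- Under Statistical & Analytical Plan and Methodology, the primary objective is to "determine if there are statistically significant differences in PFS to first line systemic therapy" between patients with and without a known fusion. A log-rank-type test "will be employed to assess the association between PFS and the presence of NTRK fusion".
- On the comparison groups: "The two groups will be matched with respect to histological subtype, sex, age (+/-5 years), and pathological tumor-node-metastasis (TNM) stage". No number of controls per case is given.
- On size: "Given the rarity of NTRK fusions among subjects with solid tumors, the sample size for this study will not be driven by powering" the study. The next sentence but one is the rule at issue: "Clinically relevant changes will be defined as increases in median survival times that are greater than 30%, regardless of confidence interval width".
- The Rationale says that the incidence "of NTRK aberrations in solid tumors is unknown as well as the natural history of NTRK-rearranged tumors". The sample size section adds: "No sample size estimate has been calculated". About 3,700 evaluable patients are expected.
- Under Statistical analyses: "The median survival rates will be reported with a 95% confidence interval". The interim looks at 1,000 and 2,000 patients estimate the fusion proportion to judge whether the matched comparison is feasible, but no minimum number of cases is set.

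**The concern.** The rule attaches a conclusion, clinical relevance, to an observed ratio of medians above 1.3 and says that precision does not enter. The same paragraph states that fusions are rare and that power does not drive the size, so precision is set aside where it is likely to be poorest.

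The plan does not say how the label and the test combine. A difference could therefore be reported as clinically relevant beside a non-significant primary comparison and a CI running from a large decrease to a large increase. The natural history of these tumours is described as unknown and publication is planned, so such a description may be taken as evidence.

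Two smaller gaps sit in the same sentence. It speaks of median survival times without saying whether PFS or the secondary endpoint OS is meant. It also covers only increases, whereas the objective concerns any difference.

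**Working it through.** **Inputs.** From the documents: threshold ratio 1.3; about 3,700 evaluable patients; matched controls. The documents give no chance rate to reproduce and no fusion count or control ratio. Assumed: 7, 18, 40 or 74 fusion patients (0.2%, 0.5%, 1.1% and 2.0% of 3,700); 1 or 4 controls per case; no true difference; exponential PFS, all events observed, independent arms.

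**Formula.** For n fusion patients and k controls each, SE of the log median ratio = (1/ln 2) × √((1 + 1/k)/n). The chance of the label is 1 − Φ(ln 1.3/SE), with ln 1.3 = 0.2624. The 95% CI around an observed 1.3 is exp(0.2624 ± 1.96 × SE).

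Example, n = 40, 1:1: SE = √(2/40)/0.6931 = 0.323; z = 0.2624/0.323 = 0.813; chance = 20.8%.

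| Fusion n | Controls | SE | z | Closed form | Simulated | CI at observed 1.3 |
|---|---|---|---|---|---|---|
| 7 | 1:1 | 0.771 | 0.340 | 36.7% | 35.9% | 0.29–5.89 |
| 18 | 1:1 | 0.481 | 0.546 | 29.3% | 29.0% | 0.51–3.34 |
| 40 | 1:1 | 0.323 | 0.813 | 20.8% | 20.8% | 0.69–2.45 |
| 74 | 1:1 | 0.237 | 1.106 | 13.4% | 13.2% | 0.82–2.07 |
| 7 | 1:4 | 0.610 | 0.430 | 33.3% | 32.2% | 0.39–4.29 |
| 18 | 1:4 | 0.380 | 0.690 | 24.5% | 23.6% | 0.62–2.74 |
| 40 | 1:4 | 0.255 | 1.029 | 15.2% | 14.4% | 0.79–2.14 |
| 74 | 1:4 | 0.188 | 1.399 | 8.1% | 7.1% | 0.90–1.88 |

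The simulated column uses 20,000 studies per setting and Kaplan-Meier medians with the midpoint convention. Taking the median as the first time the curve reaches 0.5 gives 21–36% (1:1) and 12–36% (1:4) for n = 40 to 7.

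**Cases needed.** For a CI around an observed 1.3 to exclude 1, n = (1 + 1/k) × (1.96/(ln 2 × ln 1.3))². That is 2 × 116.2 = 232.3, or 233 cases (6.3% of 3,700), at 1:1. At 1:4 it is 1.25 × 116.2 = 145.2, or 146 cases (3.9%).

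**Sensitivity, n = 7 to 40.**
- Correlation of 0.3–0.5 within matched sets, exponential margins: 16–35% (1:1) and 10–30% (1:4). A shared-frailty model instead gave about 22–38% and 13–38%, so the direction of the matching effect depends on the model.
- Weibull shape 0.7–1.5 with 0–40% censoring, over both control ratios: 5–41% with independent arms, 2–38% with correlation 0.5. Shape 2 without censoring lowers the floor to about 1% (n = 40, 1:4).

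**Label against test.** If the true increase is exactly 30%, the label is earned in about 50% of studies at any n. Schoenfeld power for the log-rank test (two-sided 5% assumed, all events observed) is then 7% to 22% at 1:1 and 9% to 32% at 1:4 for n = 7 to 40. Label and test will often disagree.

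**The case against.** The best defence is that the sentence only defines a magnitude, a threshold that does not move with precision. The study is described as descriptive, the primary objective has its own test, medians carry 95% CIs, and no success criterion or treatment decision hangs on the label. Much of this stands, and it limits the harm to wording. It does not remove the problem. A pure magnitude definition would not need the clause on interval width, and neither the test nor the CI is a condition for the label. CIs on each median are also not a CI on the ratio, which is what the rule judges.

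It is also fair that the range of 7–40 cases is assumed and that the documents cannot bound it; hence the figures at 74. The highest rates need about 7 cases, which implies roughly 2 at the first interim (7/3,700 × 1,000) and 4 at the second. The feasibility check might then stop the comparison, although without a stated minimum this is not assured.

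A reader might infer that 21–36% is the false-positive rate of the primary analysis. The documents do not support that: the label does not replace the log-rank-type test, whose type I error is unchanged. Nor do they support a claim that imprecision will be hidden, since CIs on the medians are to be reported, or that 30% is the wrong threshold.

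**Conclusion.** The concern holds as a matter of interpretation and should be fixed. Followed as written, the rule can describe a difference that is mostly noise as clinically relevant. Under the stated base case the chance rate is about 21–36% (1:1) and 14–33% (1:4) for 40 down to 7 fusion cases, and about 13% and 7–8% at 74. These figures rest on an assumed case count, control ratio, PFS shape, absence of censoring and independent arms, and the sensitivity range is wide. The conclusion does not depend on any single figure: whenever the CI around a ratio of 1.3 spans 1, the label claims more than the data show, and in the base case that is so below about 233 cases (1:1) or 146 (1:4).

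**What to change.** Delete the clause on interval width and replace the sentence with wording such as:

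> A ratio of median PFS (fusion/control) above 1.3 is the magnitude of increase regarded as clinically relevant. Any statement on clinical relevance will give the estimated ratio with its 95% CI and the result of the primary PFS comparison. If the CI includes 1, the result will be described as inconclusive. If it excludes 1 but includes 1.3, the report will say that a difference is shown but that an increase above 30% is not established. Decreases will be reported in the same way, with ratio, CI and test result. If a median is not reached, the hazard ratio with its 95% CI will be reported and the label will not be applied.

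If an endpoint other than PFS was intended, the sponsor should name it. The SAP should also state how the CI for the ratio is obtained. The documents give no threshold for a relevant decrease; if one is wanted, the sponsor must set it.

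Both limits, 1 and 1.3, are needed. With 40 cases at 1:1, an observed ratio of 2.0 has a CI of exp(0.693 ± 1.96 × 0.323), about 1.06–3.76. It excludes 1 but does not establish an increase above 30%.

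The change needs no new data. Its price is candour about small numbers. In simulation (bootstrap CI resampling matched sets), a true doubling of the median gave an observed ratio above 1.3 with a CI above 1 in only 17%, 32% and 51% of studies at 7, 18 and 37 cases with 1:1 controls, and in 26%, 43% and 70% with 1:4. Most results with few cases, true effects included, would therefore be called inconclusive, although every estimate would still be reported.
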